**Methods:**

Prior to surgery, enrolled subjects will be asked to complete a short medical history questionnaire. Subjects will then be randomized 1:1 into *Experimental* or *Control* cohorts. Randomization order will be determined by using a commercial random number generator that will be made into a log that will track group assignments. Subjects will be added to the randomization log once they have received their final surgical clearance and the surgery order is determined for their surgery date. The result of the randomization will be reported by a member of the study team to the surgeon on the day of surgery prior to the start of the first procedure.

Following the standard protocol for skin preparation in shoulder arthroplasty surgery which includes an application of 3% H2O2 with gauze, isopropyl rubbing alcohol 70% USP with gauze, and then Chloraprep in sequence, and draping with Ioban applied over the skin, the procedure will start as normal.

The skin incision will be made in standard fashion, and the knife used will be removed from the surgical field. Next, for the *Experimental* cohort, a lap sponge soaked in 3% H2O2 will be applied to the incision and allowed to sit for 3 minutes. Following the 3 minutes, the sponge will be removed, the wound will be flushed with 100 mL of normal saline, any brisk bleeding will be controlled with electrocautery, and then the exposed dermis will then be swabbed and sent for culture. In the *Control* cohort, the dermis will be swabbed and sent for culture after the skin incision is made, the knife is removed from the field, and any brisk bleeding is controlled with electrocautery.

Each subject will have the following cultures taken during the procedure, using clean instruments for each culture:

1. Negative control: Before draping the patient, a culture swab will be opened on the back table and placed in the culture tube. This is essential to evaluate the false positivity rate of our lab, as other studies have reported rates of sterile, negative control cultures having a 9% positivity rate.
2. Superficial culture #1: Following control of brisk bleeding with electrocautery as noted above, the exposed dermis will be swabbed (starting at the apex of the incision and going along the entire exposed dermis in a circular pattern twice).
3. Deep culture #1: Osteophytes are routinely removed from the humeral head after dislocation of the joint. These will be crushed and sent for culture.
4. Deep culture #2: After exposure of the glenoid, the stump of the long head of the biceps tendon is routinely excised with a portion of the labrum. We will do this in the normal fashion, and this tissue will be sent for culture.
5. Deep culture #3: Posterior and inferior labral tissue is also routinely excised and will be sent for culture following routine excision in the standard fashion.
6. Superficial culture #2: After the deltopectoral interval has been closed in standard fashion, the exposed dermis will again be swabbed as noted above.

All cultures will be sent to the lab blinded, with only the subject number and above-noted culture numbers reported to the lab rather than the location of each culture to avoid any potential bias regarding deep cultures and the negative control. We will order the standard 14-day OR hardware culture (aerobic and anaerobic) that has been recently set up at the University of Florida, which follows the recommendations of the consensus definition for periprosthetic shoulder infection published in 2019.

#### Data Analysis:

Descriptive statistics will be used to describe both the experimental and control cohort's demographic characteristics. The two cohorts' demographics and culture results will then be compared for differences with use of standard statistical tests appropriate for the data and study results. The Student T-test will be used for continuous variables and the Fisher Exact test will be used for the categorical variables. Univariate analysis will be performed between the two groups given the small number of patients in each group and the randomized design of this study.

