## 5. Specific Aims:

Specific Aim 1: Evaluate whether the hydrogen peroxide (H2O2) applied directly to the dermal tissue after the skin incision decreases the rate of dermal swabs positive for *C. acnes*.

**Summary:** Following our standard protocols for skin preparation (which includes an application of 3% H2O2, alcohol, and then Chloraprep in sequence) and draping (with Ioban applied over the skin), we will start the procedure as normal. The skin incision will be made in standard fashion, and the knife used will be removed from the surgical field. For the experimental cohort, a lap sponge soaked in 3% H2O2 will be applied to the incision and allowed to sit for 3 minutes. Following the 3 minutes, the sponge will be removed, the wound will be flushed with 100 mL of normal saline, and the exposed dermis will be swabbed and sent for culture. In the control cohort, the dermis will be swabbed and sent for culture immediately after the skin incision is made and the knife is removed from the field.

**Hypothesis:** We hypothesize that the control cohort will show results similarly to that published in the literature, with 35-70% of the cultures positive whereas the experimental cohort will have a significantly decreased rate of positivity, close to the negative control rate, likely less than 10%.

**Specific Aim 2:** Determine if H2O2 applied to the dermal tissue after skin incision will also decrease the rate of deep cultures of capsular tissue that are positive for *C. acnes*.

**Summary:** Following the procedure summarized for specific aim 1, the surgery will be carried out in a standard fashion in both cohorts. Bone, capsule, and labral tissue from around the glenoid that is routinely excised during the surgical procedure will be collected and sent for culture as described below.

**Hypothesis:** If the H2O2 is successful at decreasing the amount of contamination present at the deep dermal tissue, the rate of deep cultures positive for *C. acnes* will also decrease, supporting the hypothesis that unexpected positive deep cultures in primary shoulder arthroplasty are likely associated with contamination from the skin edge rather than due to colonization of the arthritic joint.

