## **6. Research Plan:**

**Subjects:** Once IRB approval has been obtained, up to 50 sequential male patients seen in the Hand & Upper Extremity and Sports Divisions in the Department of Orthopaedics & Rehabilitation who meet inclusion/exclusion criteria and who are boarded for primary anatomic or reverse total shoulder arthroplasty will be recruited into the study.

*Inclusion Criteria:*

- Male patients, age 40-90
- Undergoing primary anatomic or reverse total shoulder arthroplasty for glenohumeral osteoarthritis or rotator cuff arthropathy

*Exclusion Criteria:*

- Prior arthroscopic or open shoulder surgery on the ipsilateral shoulder
- Prior diagnosis of septic shoulder of the ipsilateral shoulder
- Corticosteroid injection within 3 months of the procedure
- Recently on antibiotics (within 2 weeks) prior to surgery

Assuming a rate of dermal cultures positive for *C. acnes* in the control group of 60% and a false positive rate of 10%, power analysis calculations were performed and resulted in a sample size of 13 patients per cohort needed to obtain a  $\beta = 0.2$  and an  $\alpha = 0.05$ , for a total of **26 patients**.

**Data Collection:** Under an approved HIPAA waiver, potential subjects will have their medical record and our clinical database reviewed by a member of the study staff. The following data points and information be collected for later analysis:

- Name

- Medical Record Number
- Date of Birth (to determine age)
- Gender (to determine eligibility)
- Diagnoses
- Shoulder surgical history
- Date of surgery
- Laterality
- Number of previous corticosteroid injections into the enrolled shoulder
- Past medical history of an acne breakout on the back/shoulders
- History of using prescription medications to treat acne
- Current anticoagulant or immunomodulatory medications

Additional data will be obtained during and after surgery:

- Type of implant placed (anatomic or reverse shoulder arthroplasty)
- Length of surgery
- Surgical complications
- Notes of difficulty obtaining the specified cultures
- Notes of any need to extend the skin incision during the procedure
- Postoperative wound complications

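### At about 13 men per cohort the planned Fisher exact test is valid but conservative; Boschloo's exact test, named in advance, would recover roughly 4 to 10 points of power at the design rates

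*Combined protocol and SAP*

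**What the plan says.** The combined protocol and SAP gives one rule for all comparisons between cohorts, under Data Analysis: "The Student T-test will be used for continuous variables and the Fisher Exact test will be used for the categorical variables". Culture positivity is categorical, so Fisher's test applies to it. No other test is named for these outcomes.

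The sample-size paragraph in section 6 (Research Plan) assumes a positive dermal culture rate "in the control group of 60% and a false positive rate of 10" per cent, with beta 0.2 and alpha 0.05. It reports that this "resulted in a sample size of 13 patients per cohort needed", "for a total of 26 patients". It gives neither the test behind the calculation nor whether alpha is one- or two-sided. The 10% is read here as the rate in the experimental cohort, because the Aim 1 hypothesis in section 5 expects that rate to be "close to the negative control rate, likely less than 10" per cent.

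Section 6 also allows recruitment of "up to 50 sequential male patients". Under Methods: "Subjects will then be randomized 1:1 into" the two cohorts. The order comes from a random number generator, and no blocking is described.

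**The concern.** With two small groups and a yes/no outcome, Fisher's test can take only a few p-values for any given total number of positives. Its real type I error therefore often sits well below the nominal 5%, and power is lost with it. Aim 1 rests on a single 2x2 table of about 26 men, so the loss could decide how the trial is read. At 13 v 13, a result of 7 positives in the control cohort against 2 in the experimental cohort gives Fisher p = 0.097 and Boschloo p = 0.0485. For 6 against 1 the values are 0.073 and 0.032, and for 4 against 0 they are 0.096 and 0.040.

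Correcting the stated power would not deal with this, because the same conservative test would still be used.

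**Working it through.** **Inputs.** Control rate 60%, experimental rate 10%, 13 per cohort, power 80%, alpha 0.05, ceiling of 50 men (all section 6); 1:1 allocation (Methods); Fisher's test (Data Analysis). Assumption: two-sided 0.05.

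**Step 1: the plan's own figure.** The arcsine formula is n = 2(z₀.₉₇₅ + z₀.₈₀)² / h², with h = 2·arcsin√0.6 − 2·arcsin√0.1 = 1.1287. This gives 2 × (1.960 + 0.842)² / 1.1287² = 12.3, so 13 per cohort. The pooled normal formula, [1.960·√(2 × 0.35 × 0.65) + 0.842·√(0.6 × 0.4 + 0.1 × 0.9)]² / 0.5², gives 13.04, so 14. Normal-approximation power at 13 per cohort is 79.9%. The figure of 13 is thus reproduced by a two-sided large-sample formula, but not by two-sided Fisher.

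**Step 2: both exact tests at 13 v 13.** There are 14 × 14 possible tables. For a rejection region R:

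- Size = maximum over a common rate p of Σ Bin(a; 13, p)·Bin(b; 13, p) over (a, b) in R.
- Power = Σ Bin(a; 13, 0.6)·Bin(b; 13, 0.1) over the same R.

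Fisher's R contains the tables with two-sided p ≤ 0.05. Boschloo orders tables by the same Fisher p-value and takes the largest cut-off that keeps size at or below 5%; here that is 0.0968. Its region holds all 76 Fisher tables plus 12 more, so it cannot be less powerful.

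| 13 v 13, two-sided | Fisher | Boschloo |
|---|---|---|
| Maximum size | 2.90% | 4.85% |
| Power, 60% v 10% | 71.0% | 81.3% |
| Power, 70% v 10% | 88.0% | 92.2% |
| Power, 50% v 10% | 49.0% | 64.0% |
| Power, 35% v 10% | 18.7% | 32.1% |

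The last three rows matter because section 5 expects 35–70% positive in controls.

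**Step 3: other splits and sizes, 60% v 10%, two-sided (control v experimental).**

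| Split | Fisher power | Boschloo power | Gain (points) |
|---|---|---|---|
| 13 v 12 | 73.0% | 77.9% | 5 |
| 12 v 14 | 75.4% | 79.1% | 4 |
| 14 v 12 | 73.6% | 80.1% | 6 |
| 15 v 11 | 70.8% | 80.5% | 10 |
| 14 v 14 | 74.2% | 80.7% | 6 |
| 25 v 25 | 96.0% | 97.9% | 2 |

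Fisher's maximum size also moves: 4.3% at 13 v 12, about 3.0–3.1% at the 14/12 and 15/11 splits, and 3.3% at 25 v 25. Two-sided Fisher first reaches 80% at 17 per cohort (82.7%; 78.6% at 16).

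**Step 4: one-sided 0.05, 13 v 13.** Fisher has size 2.4% and power of about 81%. Boschloo has power 86.4%, a gain of about 5 points.

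**Step 5: error rate given the total number of positives, 13 v 13, two-sided.** Fisher's is at most 4.7% at every total. Boschloo's is 9.6% at 4 positives, 7.3% at 7 and 9.7% at 9, with the mirror-image totals the same. It averages to 4.85% or less only over the binomial distribution of totals.

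**The case against.** The strongest reply is that this is a choice between two valid tests. Fisher controls type I error and is conventional for small tables. Under the null hypothesis that treatment changes no man's culture result, the total number of positives is the same under every re-randomisation, so with cohort sizes taken as fixed Fisher is the exact randomisation test. It does not need sequentially recruited men to behave as two binomial samples with a common rate. Boschloo does need that model, and Step 5 shows what follows. This stands. A reader might infer that Fisher is wrong for this design, or that its conservatism buys nothing; the documents support neither reading.

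A reader might also take a 10-point gain and arrival at 80% as assured. They are not. Unblocked randomisation of 26 men gives exactly 13/13 only about 15% of the time, a lost culture also breaks the balance, and Boschloo falls just short of 80% at 13 v 12 and 12 v 14. This stands too, though every split examined shows a gain.

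Third, recruiting up to 50 men is allowed, and 17 per cohort with Fisher would restore 80%. That is a workable alternative, but the sample-size paragraph settles on 26. Fourth, on a one-sided reading Fisher already meets the plan's target. The shortfall against 80% is therefore conditional on two-sided testing.

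**Conclusion.** The point holds as an efficiency improvement, not as an error in validity. If testing is two-sided at 0.05 and the cohorts are exactly 13 and 13, Fisher uses at most 2.9% of the 5% and has 71.0% power at 60% v 10%, against a stated 80%. Boschloo uses at most 4.85% and has 81.3%. For the same men, the gain at these rates is about 4 to 10 points across 13 v 13 and the nearby splits examined. It shrinks to about 2 points if 50 men are enrolled. The conclusion rests on the two-binomial model, on the assumed two-sided alpha, and on reading 10% as the experimental rate. No allowance is made for lost cultures, since the plan states none.

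**What to change.** Before any outcome is seen, amend Data Analysis to name Boschloo's unconditional exact test, two-sided 0.05, for the comparison of Superficial culture #1 and for the other culture comparisons, each with one result per man. Keep Fisher's p-value as a supportive result. State the sidedness of alpha in the sample-size paragraph as well, since the size of the gain depends on it.

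The change costs a sentence or two and no patients, and the test is available in standard software. The drawbacks are that clinical readers know it less well, and that its 5% guarantee holds under the binomial model and not given the observed total, where the error rate can reach 9.7% at 13 v 13. If the team prefers Fisher's randomisation basis, the alternative is to keep it and plan 17 men per cohort (34 in total), within the ceiling of 50, at the cost of 8 more men.

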#### Confidentiality:

Once all subject data is collected and verified, subject PHI will be removed from the data sheet and the data will be maintained by using assigned research identification numbers that uniquely identify each individual. A separate key code will be kept until the end of the study. Dates will also be converted to time frames. Coded data will be stored in an Excel file on a password-protected encrypted server located in the Department of Orthopaedics and

Rehabilitation. Data analysis will also be stored on this server with only the study team members having access to these files. Data will be used only in aggregate and no identifying characteristics of individuals will be published or presented. After the study is completed, the key code will be destroyed and local data will be stored with other completed research studies in a secured storage room until the appropriate time when the research files may be purged according to university policy.

## **5. Possible Discomforts and Risks:**

The only additional risk is the possible effect that application of H2O2 could have on wound healing. While some studies have shown that low-dose application of H2O2 to wounds can improve healing, there is some concern that the 3% H2O2 that will be used in this study is a high enough concentration that it can be detrimental to healing. This risk will be mitigated by rinsing away the residual H2O2 after applying it for 3 minutes to the deep dermis. Additionally, we consider this risk to be low as we often apply 3% H2O2 to surgical sites during primary and revision shoulder arthroplasty procedures after implantation of the components already to decrease the *C. acnes* bacterial burden within the joint on a case-by-case basis.

There will be no additional risk factors from culture techniques, and tissue that is routinely removed and discarded will be sent as the intraoperative deep cultures.

### Data Safety & Monitoring Plan:

A Data and Safety Monitoring Plan (DSMP) will be implemented to ensure the safety of all participants involved in the study and to ensure the validity and integrity of the data. The Principal Investigator, with the advice and assistance of the study team, will monitor all aspects of safety. As part of standard of care, all patients undergoing shoulder arthroplasty receive wound education as part of their discharge instructions. Patients also receive continuous monitoring of their wound at post-operative Day 1 and at each clinic visit. As part of the safety monitoring program for this study, subjects will have their wound evaluated for 6 weeks post-operatively to both assure real-time participant care and unbiased monitoring of adverse outcomes. Signs of delayed wound healing, including drainage, erythema, induration, and wound dehiscence will be documented by the study team.

The Study Coordinator will meet weekly with the PI to review all events related to the study. Reports of the event will include a description of the event, a classification of seriousness, assessment of potential relationship to the study, assessment of need for change in the consent or the study activities, a summary of known prior health issues, event outcome and a classification of the main organ system involved. The classification of potential relationship to the intervention is as follows:

- **Definitely** - Temporal pattern + Known or expected AE response pattern

- **Possibly** - Temporal pattern + Known or expected AE response pattern + Could not have been produced by a number of other factors
- **Unlikely** – No Temporal pattern + Known or no AE response pattern + Could have been produced by a number of other factors
- **Definitely Not** - AE for which sufficient information exists to indicate that the cause is unrelated to the study intervention

Serious Adverse Events (SAE), as defined by the FDA, will be reviewed to determine their expectedness and relatedness to the study procedures. Any SAE's that are unexpected and related will be promptly reported to the IRB according to the guidelines outlined in the UF IRB-01 "Reporting – Adverse Events, Unanticipated Problems Involving Risks to Subjects or Others, Protocol Deviations, and Other Problems". All other events, including non-serious events, will be tracked and monitored using the logs provided by the IRB. A summary of these non-serious events will be reported to the PI and IRB. All events will be assessed and monitored by the study team until their conclusion.

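### The *Definitely* and *Possibly* adverse-event causality grades do not fit their labels: *Possibly* demands everything *Definitely* does, and also that other causes be excluded

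*Combined protocol and SAP*

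**What the plan says.** The Data Safety & Monitoring Plan has the study coordinator and the principal investigator review events weekly. Each report includes an assessment of relationship to the study, and four grades of relationship to the intervention are defined:

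- The top grade, *Definitely*, is given two conditions: "Temporal pattern + Known or expected AE response pattern".
- The next grade down, *Possibly*, is given three: "Temporal pattern + Known or expected AE response pattern + Could not have been produced by a number of other factors".
- For *Unlikely* the timing does not fit, the response pattern may be known or not, and a third condition applies: "Could have been produced by a number of other factors".
- The bottom grade, *Definitely Not*, is worded differently: "AE for which sufficient information exists to indicate that the cause is unrelated to the study intervention".

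No other section redefines these grades or says which to choose when an event meets two of them.

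Three other places show where the grade could matter. Possible Discomforts and Risks states: "The only additional risk is the possible effect that application of H2O2 could have on wound healing". The data list in the Research Plan includes "Postoperative wound complications" with no condition on causality. The last paragraph of the monitoring plan uses relatedness as one of two conditions for prompt reporting: "Any SAE's that are unexpected and related will be promptly reported to the IRB".

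**The concern.** Ruling out other explanations strengthens a causal attribution. In this scale it moves an event towards the weaker label. The scale's own *Unlikely* grade shows the intended direction, because there the availability of other explanations counts against relatedness. The top two grades run the opposite way.

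What is at stake is the attribution of wound events. The team is to watch the wound for 6 weeks and record signs of delayed healing such as dehiscence, induration, erythema or drainage. All subjects have the same kind of operation, so a cause other than the peroxide may well be plausible for such a sign. Under the printed rule that is the case that meets *Definitely*. The relationship assessment also sits in the same report as the assessment of whether the consent or the study activities need to change, so a wrong label could mislead that judgement.

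**Working it through.** No sample size, power or effect size enters this point, and the plan states no figure to reproduce. The check is logical.

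**Inputs**, all from the Data Safety & Monitoring Plan. Let T = the timing fits, K = the response pattern is known or expected, and O = other factors could have produced the event.

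- *Definitely* = T and K
- *Possibly* = T and K and not O
- *Unlikely* = not T and O (K may be present or absent)

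*Definitely Not* is left out of the table because it rests on sufficient information about the cause and not on these three conditions.

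**All 8 combinations.** The last column moves the exclusion clause to *Definitely* and gives *Possibly* its opposite.

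| T | K | O | Grades met as printed | Grades met with the clause moved |
|---|---|---|---|---|
| yes | yes | yes | Definitely | Possibly |
| yes | yes | no | Definitely and Possibly | Definitely |
| yes | no | yes | none | none |
| yes | no | no | none | none |
| no | yes | yes | Unlikely | Unlikely |
| no | yes | no | none | none |
| no | no | yes | Unlikely | Unlikely |
| no | no | no | none | none |

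**Reading the first two rows.** As printed, both meet *Definitely*, one also meets *Possibly*, and neither meets *Possibly* alone. *Possibly* is a strict subset of *Definitely*. In the first row a plausible other cause does not lower the grade. In the second, an event with other causes excluded can be given either label, and choosing *Possibly* understates the evidence. These are counts of logical cases, not of patients.

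**Could lost text explain it?** Each grade is a complete bullet. Suppose the exclusion clause had dropped off the end of *Definitely*. The top two grades would then be identical, and *Possibly* would still require that other causes be excluded. The scale would still be wrong.

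**Three candidate repairs**, tested on the first two rows:

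1. Swap the two definitions. The first row becomes *Possibly* only, but the second still meets both grades. The order is right but the grades overlap.
2. Delete the word *not* from *Possibly*. The second row becomes *Definitely* only, but the first meets both grades. The grades still overlap.
3. Put the exclusion clause under *Definitely* and its opposite under *Possibly*. The first row is *Possibly* only and the second is *Definitely* only.

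Of the three, only the last makes the two grades mutually exclusive and correctly ordered.

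**The case against.** The strongest objection is that the practical consequence is close to nil. The Data Analysis section compares demographics and culture results and uses no causality grade. Wound complications are collected whatever their grade. Each report also carries "a summary of known prior health issues", so an alternative cause can be visible beside the label. Events outside prompt reporting are still tracked in logs, and non-serious ones are summarised for the investigator and the IRB. The monitoring plan does not say which grades count as related. If both top grades do, confusing them changes no reporting action. An investigator might also follow the plain meaning of the label and not the printed criteria. All of this stands as a limit on severity. It does not make the definitions coherent.

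A second objection is that the cause of the slip is unknown. The definitions may have been swapped, or a *not* may be stray in *Possibly*. Deleting it would give a sensible order if the more specific grade always took precedence, but the plan states no such rule. This stands as a reason to offer the rewording as an example only. The printed text is illogical under either explanation.

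Three stronger readings are tempting, and the documents support none of them:

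- A reader might infer that the error always overstates relatedness. It need not, because an event with other causes excluded also meets *Possibly* and could be under-labelled.
- A reader might set the known-or-expected criterion against the unexpectedness condition for prompt IRB reporting and conclude either that reports will be missed or that they are safe. Neither follows. A known pattern is enough to satisfy the criterion, and the plan judges expectedness separately from relatedness.
- A reader might want a percentage of events misgraded. The documents give no share of events with a plausible other cause, and any assumed share would only restate itself.

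**Conclusion.** Wrong as written, and minor. The two definitions contradict their labels, and nothing elsewhere in the document corrects them. Followed literally, the rule lets an event with a plausible other cause be graded *Definitely* and an event with other causes excluded be graded *Possibly*.

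The conclusion assumes only that the criteria are applied as printed and that enough is not already known to assign *Definitely Not*. Its reach is the attribution of adverse events, chiefly wound-healing events. The culture comparison and the sample size are untouched. The number of events affected cannot be estimated from the documents.

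The table shows one further gap: an event with fitting timing but no known or expected pattern meets none of the top three grades. That is a separate query for the sponsor and forms no part of this conclusion.

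**What to change.** Reconcile the two definitions so that no event can meet both and the stronger evidence earns the stronger label. One way is to move the exclusion clause from *Possibly* to *Definitely* and to end *Possibly* with the clause already used under *Unlikely*: "Could have been produced by a number of other factors". The sponsor should confirm that this is what was meant, since the documents do not show how the slip arose. Any events already classified should be regraded under the corrected wording.

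The cost is two lines in the monitoring plan plus the regrading. No change to the design, data collection or analysis is needed.

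### The causality scale has no grade for an event that follows the peroxide step but is of a new kind, so a serious event of that sort can miss the prompt IRB trigger

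*Combined protocol and SAP*

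**What the plan says.** All the relevant text is in the Data Safety & Monitoring Plan of the combined protocol and SAP.

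The scale is introduced with "The classification of potential relationship to the intervention is as follows" and has four grades:

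- The grade *Possibly* carries three conditions, worded as "Temporal pattern + Known or expected AE response pattern + Could not have been produced by a number of other factors".
- *Definitely* carries only the first two of those three, and sets no condition on other causes.
- The grade *Unlikely*, alone in allowing the response pattern to be absent, is worded as "No Temporal pattern + Known or no AE response pattern + Could have been produced by a number of other factors".
- The last grade, *Definitely Not*, is kept for an event that meets this description: "AE for which sufficient information exists to indicate that the cause is unrelated to the study intervention".

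The reporting rule follows. Serious adverse events "will be reviewed to determine their expectedness and relatedness to the study procedures". The trigger for rapid notice is then given as "Any SAE's that are unexpected and related will be promptly reported to the IRB", under a named IRB guideline that is cited but not reproduced. For the remainder, "All other events, including non-serious events, will be tracked and monitored using the logs provided by the IRB". The summary to the investigator and the IRB that comes next is described for non-serious events only.

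**The concern.** Relatedness and expectedness are meant to be separate judgements, and a prompt-report rule needs both so that it can single out surprising events that the intervention may have caused. Here the relatedness scale already contains an expectedness-like condition. Both grades that affirm a relationship ask for a pattern that is known or expected, while the reporting rule asks for an event that is unexpected. The two conditions pull against each other, most sharply for a reaction nobody has described before.

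At stake is the speed of outside notice. Safety is overseen by the principal investigator with the study team, and no independent monitor is described. The prompt report to the IRB is therefore the main rapid external check in the plan. A serious event that misses it is left to the logs, and no other IRB report is spelled out for serious events.

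**Working it through.** The plan gives no figure on this point, so there is nothing numerical to reproduce. The check applies the written definitions to every possible kind of event.

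**Inputs** (all from the Data Safety & Monitoring Plan). Each event is described by five yes/no features: temporal pattern (T), pattern known (K), pattern expected (E), could have been produced by other factors (O), and shown to be unrelated (U). That gives 2 × 2 × 2 × 2 × 2 = 32 combinations.

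**Rules as written**

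- *Definitely* = T and (K or E).
- *Possibly* = T and (K or E) and not O.
- *Unlikely* = not T, and O. Its wording on the response pattern admits either state, so it adds no restriction.
- *Definitely Not* = U.
- Prompt report of a serious event = not E, and related. The plan does not define related; I take it as *Definitely* or *Possibly*, the only affirmative grades.

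**Results for events not shown to be unrelated (U = no, 16 combinations)**

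| T | K | E | O | Grade | Prompt report if serious |
|---|---|---|---|---|---|
| yes | yes | yes | yes / no | *Definitely* / *Definitely* and *Possibly* | no (expected) |
| yes | no | yes | yes / no | *Definitely* / *Definitely* and *Possibly* | no (expected) |
| yes | yes | no | yes / no | *Definitely* / *Definitely* and *Possibly* | yes |
| yes | no | no | yes / no | none / none | no |
| no | any | any | yes | *Unlikely* | no |
| no | any | any | no | none | no |

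The fourth row is the point. A temporally linked event whose pattern is neither known nor expected fails *Definitely* and *Possibly* on the pattern, fails *Unlikely* because it has a temporal pattern, and fails *Definitely Not* because nothing shows it to be unrelated. Whether other factors could explain it makes no difference.

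With the U = yes versions added, there are 4 combinations with T = yes, K = no and E = no. Two have no grade and two are *Definitely Not*, so 0 of 4 can be graded related.

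The trigger is not empty. Among temporally linked, unexpected events not shown to be unrelated, there are 4 combinations. The 2 with a known pattern meet the trigger and the 2 without do not.

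**Would swapping two definitions cure it?** *Possibly* excludes other causes and *Definitely* does not, so the stronger grade has the weaker criteria. That is a separate drafting fault. Exchanging the two definitions leaves (K or E) in both, and the fourth row stays ungraded.

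**After the proposed change.** Let *Possibly* cover T with the intervention not ruled out (coded as not U), and let both affirmative grades count as related. Both fourth-row combinations become *Possibly*, and the trigger is met in 4 of 4 temporally linked, unexpected combinations instead of 2 of 4.

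These are counts of logical cases, not of patients, and say nothing about how often each case occurs.

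**The case against.** The strongest reply is that the link between the scale and the trigger is not written down. The scale grades relationship to the intervention, whereas the serious-event review judges relatedness to study procedures. An ungraded event is not thereby declared unrelated, and the cited IRB guideline, which is not in the documents, may require a report on other grounds. This stands as a limit. A reader might infer that a new kind of serious event could never be reported promptly, or would be reported in none of the cases. The documents do not support that, because it assumes both that this scale alone decides relatedness and that the guideline adds nothing. The reply does not remove the defect: this is the only scale given, and staff would have to depart from it to call such an event related.

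Second, the pattern condition is an either/or. A reaction known in general but not expected in this study satisfies it and can still be reported promptly. That is correct. It also rules out the inference that only events of surprising severity or frequency can reach the trigger; an event of a different but recognised kind can too.

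Third, a reader might infer from Possible Discomforts and Risks, which names wound healing as the sole added risk, that every other reaction counts as unknown. That section lists the risk of taking part. It does not define which patterns are known, and the scale does not refer to it. The gap is confined to patterns neither known nor expected.

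Fourth, such an event would not go unseen. Events are reviewed weekly with the principal investigator, each report considers whether the consent or study activities need to change, and all events are followed to their conclusion. This stands; what becomes uncertain is prompt external notice.

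**Conclusion.** The concern holds in a bounded form. As written, an event that follows the peroxide step, has a pattern neither known nor expected, and is not shown to be unrelated fits none of the four grades and cannot be graded related. If the scale governs the reporting rule, a serious event of that kind does not reach the IRB promptly through the stated trigger.

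The conclusion assumes a literal reading of the grades and that *Definitely* and *Possibly* are what the plan means by related. It makes no claim about the unseen IRB guideline.

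The size in patients cannot be given, because the documents contain no rate for such events. Exposure is small. With 1:1 randomisation, the sample-size calculation puts 13 men in the experimental cohort, and the recruitment ceiling of 50 would put about 50 / 2 = 25 there. The matter is worth correcting because it is a defective safety rule with a very cheap remedy, not because many events are expected.

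A reader might also infer that comparisons of relatedness between arms would be biased. The Data Analysis section plans comparisons of demographics and culture results and names no relatedness analysis by arm, so the documents give that inference no support.

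**What to change.** Reconcile the causality scale with the serious-event reporting rule in the Data Safety & Monitoring Plan:

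1. Stop requiring a known or expected response pattern for every affirmative grade. Define *Possibly* to cover any event with a temporal pattern to the peroxide step for which the intervention cannot be ruled out, whether or not the pattern is known.
2. Judge expectedness as a separate step, as the serious-event review already provides.
3. State that *Definitely* and *Possibly* both count as related for the prompt-report trigger, and use one term for what is being assessed (the intervention or the study procedures) in both places.

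The same edit is a convenient moment to correct the order of strictness between *Definitely* and *Possibly*, but that correction alone would not close the gap.

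The cost is a few words of text, with no new data, staff or procedures and no change to treatment. The small downside is that a few more events may be graded *Possibly* and sent promptly to the IRB.
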